## 1. INTRODUCTION

This statistical analysis plan (SAP) is based on the final protocol (v2.0) dated 12-DEC-2018. The plan covers statistical analysis, tabulations and listings of the study data to investigate the safety, tolerability and pharmacokinetics of single and multiple ascending doses of MT-6345 compared to placebo in healthy subjects.

Any statistical analysis details described in this document supersede any description of statistical analysis in the protocol.

This study was terminated due to brain changes in male rats in the 13-week tox study. Subjects were enrolled in only Part 1, Part 2 and Part 3. Some assessments which were not performed are grayed out in this SAP.

## 2. STUDY OBJECTIVE AND ENDPOINTS

### 2.1. Study Objectives

#### 2.1.1. Primary Objective

- To evaluate the safety and tolerability of single and multiple ascending oral doses of MT-6345 administered to healthy subjects.

#### 2.1.2. Secondary Objectives

- To investigate the PK profile of MT-6345 following single and multiple ascending oral doses administered to healthy male subjects.
- To investigate the effect of food ~~and/or~~ on the PK profile of MT-6345 following a single oral dose administered to healthy male subjects.
- To investigate the effect of gender on the PK profile of MT-6345 following a single oral dose administered to healthy female subjects.
- To investigate the effect of MT-6345 drug concentration on QT prolongation and QTc interval following single and multiple oral doses administered to healthy subjects.

#### 2.1.3. [REDACTED]

### 2.2. Study Endpoints

#### 2.2.1. Primary Endpoints

##### Safety assessments

- Incidence and severity of adverse events (AEs).

- Vital signs (supine blood pressure, pulse rate, respiratory rate and oral body temperature).
- ECG parameters (including heart rate and cardiac intervals: PR, QRS, QT and calculation of corrected QT interval using Fridericia's formula [QTcF]).
- Clinical laboratory assessments (including haematology, biochemistry, coagulation and urinalysis).
- Physical examination.
- Part 3 only, in addition: specialist eye examination findings

## 2.2.2. Secondary Endpoints

### Pharmacokinetic assessments:

Plasma concentration versus time profile of MT-6345 after single and multiple dosing.

The following PK parameters will be calculated for MT-6345 after single dosing:

- Maximum plasma concentration after administration ( $C_{max}$ )
- Time to maximum plasma concentration ( $t_{max}$ ).
- Plasma terminal elimination half-life- ( $t_{1/2}$ ).
- Area under the plasma concentration-time- curve from time zero to 24 hours ( $AUC_{0-24h}$ ).
- Area under the plasma concentration-time- curve from time zero to the last measurable concentration ( $AUC_{0-last}$ ).
- Area under the plasma concentration-time curve from zero up to infinity with extrapolation of the terminal phase ( $AUC_{0-\infty}$ )
- Terminal elimination rate constant (Kel).
- Mean residence time (MRT).
- Apparent oral clearance (CL/F).
- Apparent volume of distribution during terminal phase ( $Vz/F$ )
- Apparent volume of distribution at steady state ( $Vss/F$ )

The following PK parameters will be calculated for MT-6345 after multiple dosing where appropriate:

- $C_{max}$ .
- $t_{max}$ .
- $t_{1/2}$ .
- Area under the plasma concentration-time- curve over the dosing interval ( $AUC_{0-\tau}$ ).
- $AUC_{0-last}$ .
- $AUC_{0-\infty}$ .
- Kel.
- MRT.
- CL/F.

- Apparent volume of distribution at steady state ( $V_{ss}/F$ ).
- Apparent volume of distribution during terminal phase ( $V_z/F$ )
- Linearity factor (LF).
- Accumulation ratio (AR).
- Urinary excreted amount of test compound (Ae).
- Urinary excreted amount of test compound expressed as a percentage of the dose administered (Ae%).
- Renal clearance ( $CL_R$ ).

QT interval assessments

Continuous 12-lead Holter data will be obtained from subjects in Parts 1 and 3. Data will be analysed following completion of the study to investigate the potential effect of MT-6345 on QTc interval or stored for future analysis.

2.2.3. [REDACTED]

### 3. STUDY DESIGN

This was a Phase I, randomised, double-blind, placebo-controlled, single-centre study, comprising five parts. It was planned to randomise 100 subjects. If required, one additional cohort of 8 subjects and one cohort of 12 subjects may have been added to Parts 1 and 3, respectively.

The study sequences are illustrated in Figure 1 and Figure 2.

#### 3.1.1. Planned Study Design

##### Part 1: Single ascending dose (SAD)

Up to 48 healthy Caucasian males, aged 18 to 55 years who meet the study criteria will be allocated to six cohorts of 8 subjects each. One additional cohort of 8 male subjects may be enrolled (e.g., in case the mean maximum observed human exposure value at the highest dose is at least 50% lower [i.e., 22,625 ng.h/mL] than the AUC at the NOAEL in rat [45,250 ng.h/mL]). In each cohort, 6 subjects will be randomised to receive a single dose of MT-6345 and 2 subjects will be randomised to receive a matching dose of placebo.

All cohorts will have 2 sentinel subjects of whom 1 subject will receive MT-6345 and 1 subject

will receive matched placebo. The remaining 6 subjects, of whom 5 subjects will receive MT-6345 and 1 subject will receive placebo, will be dosed at least 24 hours following the sentinel subjects.

The dose levels are planned to be administered in ascending order. Subjects will receive a single dose of MT-6345 or placebo in a fasted state (for at least 10 hours). Progression to the next dose level, and dose selection, will be based on all available safety and tolerability data up to at least 48 hours post-dose and available PK data (up to at least 24 hours post-dose) from a minimum of 6 subjects (MT-6345  $n \geq 4$ ) in the preceding dose cohort.

The dose administered to Cohort 1 will be [REDACTED]. The anticipated dosing schedule is [REDACTED] [REDACTED] [REDACTED] and [REDACTED]. The maximum dose in Part 1 (SAD) is anticipated to be [REDACTED] however, this will be selected based upon emerging PK, safety and tolerability data from previous cohorts, but will not exceed an individual exposure limit of 45,250 ng.h/mL (AUC0-24h).

The maximum number of capsules which are planned to be administered in this group are up to 24 x [REDACTED] capsules (size 3) of MT-6345 or matching placebo, in the [REDACTED] cohort. MTPE has experience with a first-in-man study (MT-3995-E01, EudraCT: 2009-014884-38) where the SAD part of the study required the administration of 32 x size 3 capsules (diameter 5.82 mm) at the highest dose level. This dose level was administered with no significant impact on the subjects or study. Subjects will be permitted additional water to help swallow the capsules if necessary. At Screening all subjects will be questioned on whether they have any known history of difficulty in swallowing a large size or number of capsules. Any subject with such a history will be excluded from the study as per exclusion criterion 24.

Continuous 12-lead Holter data will be obtained from subjects in Part 1. Data will be analysed following completion of the study to investigate the potential effect of MT-6345 on QTc interval or stored for future analysis.

## Part 2: Food effect

A single cohort from Part 1 (anticipated to be Cohort 3; [REDACTED] MT-6345) will be selected to return for a second treatment period to investigate the effect of food (after a Food & Drug Administration [FDA]-approved high-fat breakfast)[14] on the PK of MT-6345. There will be a minimum of 15 days between the last dose administration in Part 1 and the first dose administration in Part 2. Subjects in Part 2 will receive the same dose (active or placebo) that they received in Part 1.

The dose and cohort selected for Part 2 will not be confirmed until safety, tolerability and PK data from the intended dose level in Part 1 has been reviewed and deemed acceptable. The intention is for all 8 subjects to be dosed sequentially on the same day.

### **Part 3: Multiple ascending dose (MAD)**

A total of 36 healthy Caucasian males, aged 18 to 55 years, who meet the study eligibility criteria, will be allocated to three cohorts of 12 subjects each. An additional cohort of 12 healthy male subjects may be enrolled (e.g., in case the mean maximum observed human exposure value at the highest dose is at least 50% lower than the AUC at the NOAEL in rat [22,625 ng.h/mL]). In each cohort, 9 subjects will be randomised to receive multiple doses of MT-6345 and 3 subjects will be randomised to receive matching doses of placebo.

The current dosing regimen in Part 3 is anticipated to be 14 days multiple-dose administration of MT-6345 or placebo capsules once daily on Days 1 to 14. The duration of dosing may be altered based upon emerging PK data but will not exceed 28 days.

The MAD cohorts may consist of sentinel dosing (1 subject will receive MT-6345 and 1 subject will receive matched placebo). Whether sentinel cohorts are needed will be decided based upon review of prior SAD and MAD cohorts. The remaining 10 subjects, of whom 8 subjects will receive MT-6345 and 2 subjects will receive placebo, will be dosed when the first MT-6345 dosed sentinel subject is predicted to have reached steady state concentration of MT-6345 (five half-lives).

The dose levels are planned to be administered in ascending order. Progression to the next dose level, and dose selection, will be based on the safety, tolerability and available PK data from Part 1 and the preceding dose cohort in Part 3 (safety and tolerability data up to 72 hours after the last dose and available PK data up to 24 hours after the last dose, from a minimum of 10 subjects [MT-6345  $n \geq 7$ ] in the preceding dose cohort).

The anticipated doses are [REDACTED] and [REDACTED] once daily; however, the choice of doses will be reviewed and may be altered based on the emerging data.

Continuous 12-lead Holter data will be obtained from subjects in Part 3. Data will be analysed following completion of the study to investigate the potential effect of MT-6345 on QTc interval or stored for future analysis.

In Part 3, subjects will be admitted to the [REDACTED] 2 days prior to the first dosing (evening of Day -2). The first dose of MT-6345 or placebo will be administered on the morning of Day 1. Subjects will remain in the [REDACTED] until 72 hours post-dose after the final dose. Subjects will return for outpatient visits (if the subjects are not confined to the [REDACTED]) and PK blood samples will be taken at 5 and 8 days after last dosing. Subjects will return to the [REDACTED] 14 days after last dosing for a Follow-up Visit.

### **Part 4: Gender effect**

One cohort of eight healthy Caucasian females, aged 18 to 55 years, who meet the study

eligibility criteria, will be investigated to determine the effect of gender on PK following a single oral dose of MT-6345. The anticipated dose is [REDACTED] however, this may be modified based on emerging PK, safety and tolerability data from Part 1. The dose selected will not be confirmed nor administered until safety, tolerability and PK data from the intended dose level in Part 1 has been reviewed and deemed acceptable. Subjects will be randomised (MT-6345, n=6: placebo, n=2) to receive a single dose of MT-6345 or placebo in a fasted state (for at least 10 hours).

#### **Part 5: Race effect – Japanese**

One cohort of eight healthy Japanese males, aged 18 to 55 years, who meet the study eligibility criteria, will be investigated to determine the effect of race on PK following a single oral dose of MT-6345. The anticipated dose is [REDACTED] however, this may be modified based on emerging PK, safety and tolerability data from Part 1. The dose selected will not be confirmed nor administered until safety, tolerability and PK data from the intended dose level in Part 1 has been reviewed and deemed acceptable. Subjects will be randomised (MT-6345, n=6: placebo, n=2) to receive a single dose of MT-6345 or placebo in a fasted state (for at least 10 hours).

[figure not shown]
Subjects in Part 1 will be admitted to the [REDACTED] 2 days prior to dosing (evening of Day -2) in order to begin Holter Monitoring on Day -1 and [REDACTED].

Subjects in Parts 2, 4 and 5 will be admitted to the [REDACTED] 1 day prior to dosing (Day -1). MT-6345 or placebo will be administered on the morning of Day 1. Subjects in Parts 1, 2 and 4 will remain in the [REDACTED] until 48 hours post-dose, i.e., the morning of Day 3. Subjects will return for outpatient visits and PK blood samples will be taken at Day 4, Day 6 and Day 9. Japanese subjects in Part 5 will remain in the [REDACTED] until 120 hours post-dose, i.e., the morning of Day 6.

Subjects will return to the [REDACTED] on Day 15 for a Follow-up Visit.

[figure not shown]
The same dose will be used for each cohort in Parts 2, 4 and 5.

**Figure 1** Study design scheme for Parts 1, 2, 4 and 5

\* Japanese subjects in Part 5 will be discharged on Day 6

**Figure 2** Study design scheme for Part 3

### **3.1.2. Actual Study Outcome**

This study was terminated due to brain changes in male rats in the 13-week tox study. Subjects were enrolled in only Part 1, Part 2 and Part 3. Along with this, some assessments were not performed in these parts and they are grayed out in this SAP.

### **3.2. Schedule of Study Procedures**

Study assessments are summarised in the time and events schedule (Table 1, 2 and 3).

**Table 1 Time and events schedule for Parts 1, 2\*, 4 and 5**

Study Day	SCR	ADM	Treatment day												FU 15									
	-28 to -3/-2	-2/-1	1	Pre	0	0.5	1	1.5	2	3	4	5	6	8	12	16	24	48	72	120	192			
Time point hours)	<----->												>											
Confinement 																								
Outpatient	X																							
Randomisation			X																					
IMP administration			X																					
Informed consent	X																							
Demography and medical history	X																							
Inclusion/exclusion criteria	X	X	X																					
Body weight and BMI	X	X																						
Height	X																							
Drug and alcohol screening 	X	X																						
Serology 	X																							
Pregnancy test 	X	X																						
FSH blood test 	X																							
Physical examination 	X																							
Eye examination	X																							
Supine blood pressure, pulse and respiratory rate	X	X	X																					
Oral temperature	X	X	X																					
12-lead ECG 																								
12-lead ECG (standard safety) 	X	X	X																					

Abbreviations: ADM=admission; BMI=body mass index; ECG=electrocardiogram; FSH=follicle stimulating hormone; FU=Follow-up Visit;

HIV=human immunodeficiency virus; IMP=Investigational Medicinal Product.

PK=pharmacokinetic; QTcF=corrected QT interval using Fidericia's formula; SCR=Screening Visit.

1. Subjects admitted on the evening of Day -2 for Part 1, and the morning of Day -1 for Parts 2, 4 and 5. Subjects will be discharged on the morning of Day 3.
2. Urine drugs of abuse screen will include tests for methadone, cocaine, tetrahydrocannabinol, benzodiazepines, barbiturates, amphetamines and opiates. Carbon monoxide and alcohol breath tests will also be performed.
3. Serology testing for hepatitis B surface antigen, hepatitis B core antibody, hepatitis C antibodies and HIV 1/2 antibodies.

Confidential

Page 15 of 38

**Table 2 Time and events schedule for Part 3**

Study Day	SCR	Treatment day	FU
	-28 to -3	Day -2 to maximum of Day 31 (confinement period)	5 and 8 days after last dose
Outpatient visit	X		X
Informed consent	X		X
Demography and medical history	X		
Inclusion/exclusion criteria	X		
Body weight and BMI	X		
Height	X		
Drug and alcohol screening 	X		
Serology 	X		
Physical examination 	X		
Eye examination 	X		
Supine blood pressure, pulse and respiratory rate	X		
Oral body temperature	X		
12-lead ECG (safety)	X		
Haematology, biochemistry, coagulation and urinalysis	X		
Blood sampling for PK 			
Adverse events			
Concomitant medication			

Abbreviations: BMI=body mass index; ECG=electrocardiogram; PK=blood sample for PK; FU=Follow-up Visit; HIV=human immunodeficiency virus; SCR=Screening Visit.

1. Urine drugs of abuse screen will include tests for methadone, cocaine, tetrahydrocannabinol, benzodiazepines, barbiturates, amphetamines and opiates. Carbon monoxide and alcohol breath tests will also be performed.

2. Serology testing for hepatitis B surface antigen, hepatitis B core antibody, hepatitis C antibodies and HIV 1/2 antibodies.

3. Full physical examination will be performed at Screening and Follow-up. At other times, a targeted (symptom driven) physical examination of relevant body system(s) will be performed following physician assessment if the subject reports feeling unwell or an adverse event.

4. Conducted by a Consultant Ophthalmologist. Further details can be found in Section 6.5.1. Screening examination may be performed at any time between Day -28 and Day -3. Follow-up examination may be performed at any time between last dosing and the Follow-up Visit.

5. PK blood samples for MT-6345 will be collected during the confinement period (see Table 3). Subjects will return for outpatient visits and PK blood samples will be taken 5 and 8 days after the last dose (120 and 192 hours after the last dose), and at FU 14 ± 1 days after last dose (336 hours after last dose).

Confidential

Page 17 of 38

**Table 3** Time and events schedule for Part 3 (confinement period)

Study Day	ADM	Treatment day													
		1	2	3	4	5	6	7	D 	8	9	10	11	12	13
Time point (hours)	Pre	0	0.5	1	1.5	2	3	4	5	6	7	48	72	96	120
Blood sampling for PK 	X	X	X	X	X	X	X	X	X	X	X	X	X	X	X
Urine sampling for PK 	█	█	█	█	█	█	█	█	█	█	█	█	█	█	█
Adverse events															
Concomitant medication															

Abbreviations: ADM=admission; BMI=body mass index; ECG=electrocardiogram; IMP=Investigational Medicinal Product; LDD=last day of dosing; MDD=midpoint dosing day;

PK=pharmacokinetic; QTcF=corrected QT interval using Fridericia's formula.

1. e.g. if duration of dosing is 14 days then should be on Day 7 (+/- 2 days)
2. Subjects will receive a once daily dose of MT-6345 for at least 14 days. Dosing can be extended out as far as Day 28, so the day before the LDD can be Day 13 up to a maximum of Day 27.
3. The LDD will be Day 14, at a minimum. Dosing can be extended out as far as Day 28.
4. Subjects admitted on the evening of Day -2; assessments will be performed on Day -1. Subjects will be discharged 72 hours after the LDD (Day 17 at minimum, Day 31 at maximum).
5. Conducted by a Consultant Ophthalmologist. Further details can be found in Section 6.5.1
6. Urine drugs of abuse screen will include tests for methadone, cocaine, tetrahydrocannabinol, benzodiazepines, barbiturates, amphetamines and opiates. Carbon monoxide and alcohol breath tests will also be performed.
7. Vital sign assessments to be conducted at pre-dose on Day 2 to the LDD.
8. Continuous ECG will be collected from approximately 24 hours prior to dosing on Day -1 until pre-dosing on Day1; and from pre-dose on the LDD to 24 hours after last dosing (LDD +1). ECG extractions to occur at each PK blood sampling time point during this period.
9. A 12-lead ECG (heart rate and cardiac intervals: PR, QRS, QT and QTcF) will be performed at Day -1 (-0.5, 1, 2, 3 and 8 hours relative to expected dose time on Day 1); Days 1, 8 and LDD (at pre-dose, 1, 2, 3 and 8 hours post-dose); Days 2 to 7 (pre-dose); Days 9 to the day before the LDD (pre-dose); and 24 hours and 72 hours after the LDD (LDD +1 and LDD +3).
10. If dosing is extended beyond 14 days, a blood sample will be taken on Day 14 and every 7 days thereafter.
11. PK blood samples for MT-6345 will be collected on Day 1 (pre-dose and at 0.5, 1, 1.5, 2, 3, 4, 5, 6, 8, 12 and 16 hours post-dose), Day 2 to LDD -1 (pre-dose), LDD (pre-dose and at 0.5, 1, 1.5, 2, 3, 4, 5, 6, 8, 12 and 16 hours post-dose), and on LDD +1 (24 hours post last dose), LDD +2 (48 hours post last dose) and LDD +3 (72 hours post last dose).

13. PK urine samples for MT-6345 will be collected at Day-1 (-24 hours 0 hours), Day1 (0 hours to 24 hours) and LDD(0 hours to 24 hours).

### **3.3. Sample Size and Power Considerations**

#### **3.3.1. Planned Sample Size and Power Considerations**

It is planned to enrol up to 100 subjects in this study, which may be extended to 120 subjects if additional cohorts are included in Parts 1 and 3 of the study:

Part 1: 48 healthy male Caucasian subjects allocated to one of six dose cohorts comprising 8 subjects each. An additional cohort of 8 subjects may be enrolled.

Part 2: 8 healthy male Caucasian subjects (cohort selected from Part 1).

Part 3: 36 healthy male Caucasian subjects allocated to one of three dose cohorts comprising 12 subjects each. An additional cohort of 12 subjects may be enrolled.

Part 4: 8 healthy female Caucasian subjects.

Part 5: 8 healthy male Japanese subjects.

There are 8 subjects in each cohort from Parts 1, 4 and 5, and 12 subjects in each cohort from Part 3 (randomised in a 3:1 ratio to MT-6345:placebo). All cohorts in Part 1 will include 2 sentinel subjects dosed on the first dosing day, of whom one will receive active drug and one will receive placebo. The MAD cohorts may consist of sentinel dosing (1 subject will receive MT-6345 and 1 subject will receive matched placebo). Whether sentinel cohorts are needed will be decided based on review of prior SAD and MAD cohorts. The remaining 10 subjects, of whom 8 subjects will receive MT-6345 and 2 subjects will receive placebo, will be dosed when the first MT-6345 dosed sentinel subject is predicted to have reached steady state concentration of MT-6345 (five half-lives).

The sample size is not based on a formal statistical evaluation but was considered to be adequate to meet the objectives of the study and is a typical size for first-in-man SAD and MAD studies. A sufficient number of subjects will be screened to ensure that the planned sample size will be achieved.

#### **3.3.2. Actual Sample Size**

This study was terminated due to brain changes in male rats in the 13-week tox study. Subjects were enrolled in only Part 1, Part 2 and Part 3. 52 subjects were actually randomized as follows.

Part 1: 44 subjects in total; 8 subjects for [REDACTED] and [REDACTED] cohorts respectively, and 6 subjects for [REDACTED] and [REDACTED] cohorts, respectively.

Part 2: 6 subjects returned to received the same [REDACTED] dose as in Part 1 (active or placebo), are therefore not unique patients and are not counted again in the total number of exposed subjects.

Part 3: 8 subjects in the [REDACTED] cohort

#### 4. PLANNED ANALYSIS

This SAP will be finalized before database lock. Final data analysis will be conducted after database lock.

#### 5. ANALYSIS POPULATIONS

Analysis Population	Definition
Randomised Population (RAND)	All subjects randomised.
Safety analysis set (SAF)	All randomized subjects who received at least one dose of IMP.
PK analysis set (PKPOP)	All subjects who complete the study without having a major emesis episode within 2 hours of dosing on that day and have evaluable PK parameters. The PK data from subjects with emesis within 2 hours of dosing may be analysed separately.

The SAF or RAND will be used for study population-related evaluations. The SAF will be used for all safety evaluations. The PKPOP will be used for the PK analyses.

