#### 4.5 Withdrawal of individual subjects

Subjects will be withdrawn from the study for the following reasons:

- The subject wishes to withdraw from further participation.
- The subject is significantly noncompliant with the Protocol.
- Continuing in the study would be detrimental to the subject's safety in the opinion of the Investigator, e.g.,
  - The subject experiences intolerable AEs or serious adverse events (SAEs)
  - The subject has clinically significant changes in safety parameters at any of the post-dose time points, as confirmed with a repeat assessment performed as soon as possible after the initial out-of-range result.
  - The subject has an increase in QTcF to  $\geq 500$  ms or increase of  $\geq 60$  ms from baseline (pre-dose on Day 1), as confirmed with three consecutive ECGs taken at least 5 minutes apart in a 30-minute period.
  - Development of any clinically significant liver dysfunction, as follows:
    - ALT or AST  $>8 \times$  ULN.
    - ALT or AST  $>5 \times$  ULN for more than 2 weeks.
    - ALT or AST  $>3 \times$  ULN in conjunction with elevated total bilirubin  $>2 \times$  ULN, or international normalised ratio  $>1.5$ .
    - ALT or AST  $>3 \times$  ULN with appearance of fatigue, nausea, vomiting, right upper quadrant pain or tenderness, fever, rash and/or eosinophilia ( $>5\%$ ).
  - Part 3 only: the subject has clinically significant changes to the corneal epithelium on the eye examinations conducted by a Consultant Ophthalmologist. Clinical significance will be judged by the Investigator.
- Pregnancy in a female subject.

In addition, a subject may be withdrawn at any time for reason(s) other than those listed here. If IMP is discontinued in a subject, then the subject may still undergo all other study procedures but will not receive the IMP.

If a subject is withdrawn from the study prematurely, the date the IMP is discontinued and the reason for withdrawal will be recorded on the electronic case report form (eCRF).

In case of withdrawal of a subject from the study, the Follow-up Visit assessments should be performed, as far as possible (Section 5.2.4).

Reporting as an SAE must be considered in cases where the AE has led to a withdrawal from the study or the withdrawal is for a safety reason and, therefore, may be medically important, in accordance with Section 8.2.

Any unresolved AE or SAE will be followed up according to Section 8.9.

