- Serology testing for hepatitis B surface antigen, hepatitis B core antibody, hepatitis C antibodies and HIV 1/2 antibodies.
- Female subjects only (Part 4). A serum pregnancy test will be performed at Screening and a urine pregnancy test at all other time points.
- Females only (Part 4). The sample taken for biochemistry analysis will be used to measure FSH.
- A full physical examination will be performed at Screening and Day 15 FU. At other times, a targeted (symptom driven) physical examination of relevant body system(s) will be performed following physician assessment if the subject reports feeling unwell or an adverse event.
- Continuous 12-lead Holter data will be obtained from subjects in Part 1. Continuous ECG will be collected from approximately 24 hours prior to dosing (Day -1) to 24 hours post-dosing (Day 2). Electrocardiogram extractions will occur at each PK blood sampling time point during this period.
- A 12-lead ECG (heart rate and cardiac intervals: PR, QRS, QT and QTcF) will be performed at Day -1 (-0.5, 1, 2, 3, 8) and Day 1 (pre-dose, 1, 2, 3, 8 hours post-dose) and Day 2 (24 hours post-dose).
- PK blood samples for MT-6345 will be taken at pre-dose, 0.5, 1, 1.5, 2, 3, 4, 5, 6, 8, 12, 16, 24, and 48 hours post-dose. Subjects will return for outpatient visits and PK blood samples will be taken at 72 (Day 4), 120 (Day 6), 192 (Day 9) and 336 hours (Day 15 FU) post-dose.

Europe/Mitsubishi Tanabe Pharma Europe Ltd  
STUDY PROTOCOL

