**5.2.4 Follow-up**

**5.2.4.1 Follow-up (Parts 1, 2, 4 and 5)**

Subjects will return to the clinic on Day 15 ± 1 day for a Follow-up Visit. The cohort of subjects selected for Part 2 will not attend the Follow-up Visit following their first treatment period (Part 1) but will attend a Follow-up Visit at Day 15 ± 1 day following their second treatment period. The following assessments will be performed (refer to Table 2 for further details):

- Physical examination (including weight, BMI and eye examination).
- Vital signs (including supine blood pressure, pulse rate, respiratory rate and oral body temperature).
- 12-lead ECG.
- Routine laboratory evaluations (haematology; biochemistry; coagulation; urinalysis).
- Urine pregnancy test for females only.
- PK blood sampling for MT-6345.
- AE and concomitant medication recording.

---

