## 11.5 End of study and site closure

The end of the study is defined as the last visit for the last subject. Upon completion of the study, or if the study or an Investigator site is prematurely discontinued, the following activities, where applicable, must be conducted by the Study Monitor in conjunction with the Investigator:

- Return of all study data to the Sponsor.
- Completion of data clarifications and/or resolutions.
- Accounting, reconciliation, and final disposition of used and unused IMP.
- Review of Investigator site study records for completeness.

Any unresolved AE or SAE will be followed up according to Section 8.9.

Europe/Mitsubishi Tanabe Pharma Europe Ltd

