### 8.3.2. Pharmacokinetic Parameters

The pharmacokinetic parameters listed in Section 2.2 will be calculated for each subject on active dose using a non-compartmental model. The pharmacokinetic parameters will also be listed. The plasma pharmacokinetic parameters will be summarized by each dose group and fed state. The plasma pharmacokinetic parameters will also be listed for each part.

The urinary pharmacokinetic parameters will be summarized for each dose level. The urinary pharmacokinetic parameters will also be listed.

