### 8.3.3. Dose Proportionality

Dose proportionality will be assessed by  $AUC_{0-\text{last}}$ ,  $AUC_{0-\infty}$  and  $C_{\max}$  for single dose using a power model. A schematic representation of this is outlined below:

$$AUC_{0-\text{last}} \text{ or } AUC_{0-\infty} \text{ or } C_{\max} = e^{\mu} \cdot Dose^{\beta} \cdot e^{\varepsilon}$$

The following linear model will be fitted to the log-transformed parameters of interest:

$$\log_e (AUC_{0-\text{last}} \text{ or } AUC_{0-\infty} \text{ or } C_{\max}) = \mu + \beta \cdot \log_e (Dose) + \varepsilon$$

Where  $\mu$  and  $\beta$  are the regression intercept and slope coefficients and  $\varepsilon$  is the error term; assumed to be normally distributed.

The estimate obtained for  $\beta$  is a measure of dose proportionality. Dose proportionality will be

concluded if the 95% CI for  $\beta$  includes the value 1. The parameter estimates and the 95% CIs will be produced.

The evaluation of the model fit will be done by lack-of-fit. In the case where dose-proportionality across all investigated dose groups cannot be established, additional exploratory analysis will be done by either fitting power model on subgroup of investigated dose groups or other data-driven analysis, if deemed appropriate.

To evaluate dose proportionality graphically the following plots will be produced:

- Individual plots of  $AUC_{0\text{-last}}$ ,  $AUC_{0\text{-}\infty}$  and  $C_{\max}$  versus dose levels on linear and log scales (with the fitted linear regression line for log scales)
- Individual plots for  $AUC_{0\text{-last}}/\text{dose}$ ,  $AUC_{0\text{-}\infty}/\text{dose}$  and  $C_{\max}/\text{dose}$  by dose level

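### The PK analysis set requires study completion, which is not defined per subject, so an early leaver with an evaluable Cmax is dropped from the PK summaries and the power model

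*SAP*

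**What the plan says.** SAP section 5 admits to the PK analysis set (PKPOP) "All subjects who complete the study without having a major emesis episode within 2 hours of dosing on that day", and also requires evaluable PK parameters. It then assigns PKPOP to the PK analyses. Protocol 10.2 has the same definition, so there is no softer rule to fall back on.

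The nearest text on completion is in Protocol 11.5: "The end of the study is defined as the last visit for the last subject". That is a milestone for the whole trial. Protocol 4.5 separates stopping drug from leaving the study: "If IMP is discontinued in a subject, then the subject may still undergo all other study procedures". It does not say whether such a subject counts as a completer.

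SAP 8.3.2 says that PK parameters "will be calculated for each subject on active dose using a non-compartmental model" and listed, with no completion condition. SAP 8.3.3 assesses dose proportionality "for single dose using a power model", fitted to AUC0-last, AUC0-∞ and Cmax. That is a PK analysis, so it runs on PKPOP.

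**The concern.** Completion and evaluability are separate conditions, and a subject must meet both. Completion says nothing about whether a given parameter was measured. Cmax and AUC0-24h are settled by the first day of sampling, while the last single-dose visit is on Day 15. A subject can therefore have sound values for both and still lose them from the summaries by missing a late visit.

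The condition does have a use: it screens out AUC0-last values cut short by early departure. But it acts on the whole subject, so good parameters go with the bad ones.

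Because the term is undefined, someone must also decide who completed. SAP 7.4 allows PK data-handling decisions both before and after unblinding, so membership could be settled once concentrations are visible.

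**Working it through.** **1. Counts that the plan gives.** SAP 3.3.2 reports 44 subjects in Part 1 and 8 in Part 3, and 44 + 8 = 52, the stated number randomised. With six Part 1 cohorts of 8 or 6, the only solution is 4 × 8 + 2 × 6 = 44. Cohorts of 8 have 6 active subjects. The split in the cohorts of 6 is not given; assuming 4 or 5 active, the Part 1 active total is 4 × 6 + 2 × 4 = 32 to 4 × 6 + 2 × 5 = 34.

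**2. Sampling.** Protocol Table 2 states: "PK blood samples for MT-6345 will be taken at pre-dose, 0.5, 1, 1.5, 2, 3, 4, 5, 6, 8, 12, 16, 24" and 48 hours, then 72, 120, 192 and 336 hours. That is 13 samples to 24 h, 14 to 48 h, 17 to 192 h and 18 in all. The 18 agrees with Protocol Table 6.

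**3. The rule applied to one subject.** Take a Part 1 subject on active drug, without emesis, who leaves after the 48 h sample.
- Emesis condition: met.
- Evaluable PK parameters: met for Cmax and AUC0-24h, with all 13 samples to 24 h in hand.
- Completes the study: not met on the natural reading.
- Result: out of PKPOP. Cmax is lost from the summaries and the power model, and AUC0-24h from the summaries.

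**4. Is there a rule that brings this subject back?**
- Protocol 3.4 calls a subject evaluable if the data suffice, but for dose review meetings.
- SAP 7.1.3.1 and 7.4 deal with invalid data, and SAP 7.3 with missing data. They act on values, not on set membership.
- SAP Appendix 1 withholds AUC0-∞ and related parameters when Kel is missing. Cmax and AUC0-last are not on that list, so the SAP already handles part of evaluability by parameter.
- SAP 8.1.1 summarises discontinuations.

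None restores a non-completer.

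**5. Why evaluability differs by parameter.** For a mono-exponential decline, the share of AUC after time T is 2^(−T/t½). No half-life is documented. At assumed half-lives of 6, 12, 24 and 48 h, the share after T = 48 h is 0.4%, 6.3%, 25% and 50%. A profile ending at 48 h may therefore be useless for AUC0-last, while Cmax is unaffected.

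**6. Effect on the only inferential PK output, the slope β.** The 95% half-width is t(0.975, n−2) × σ / √Sxx, with Sxx the sum of squares of log dose. Doses are redacted, so two spacings were assumed: two-fold steps, and the maximum permitted steps of 5, 4, 3, 3 and 3. Worked case: two-fold steps with 6, 6, 6, 6, 4, 4 active subjects.
- n = 32: Sxx = 86 × (ln 2)² = 41.32, so the half-width is 2.042σ/6.428 = 0.3177σ.
- Remove one subject at the top dose, n = 31: Sxx = 78.19 × (ln 2)² = 37.57, so the half-width is 2.045σ/6.129 = 0.3337σ.
- Ratio 1.050, a widening of 5.0%.

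Over both spacings, every cohort position and 32 to 36 active subjects, one exclusion widens the interval by about 0.1% (middle doses) to 5% (end doses).

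**7. Effect within a cohort.** Going from 6 to 5 active subjects raises the standard error of a log-mean by √(6/5) = 1.095, or 9.5%. SAP 6.1 reports neither standard errors nor confidence intervals for cohort PK parameters, so this would not appear in any planned table.

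**The case against.** The strongest reply is that nothing is shown to have been lost. No non-completer is documented. Protocol 4.5 and 7.2 let the sponsor and investigator replace subjects withdrawn for reasons unrelated to treatment, on the same treatment. Individual values stay in the listings. SAP 6.2 plans no statistical tests, and SAP section 10 drops the food-effect mixed model. Evaluability also has a home in the PK data-handling document of SAP 7.4. All of this stands, and it sets the severity. It does not supply the missing definition or restore an evaluable Cmax. Replacement is discretionary, and it does not bring the departed subject's data back into the set.

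Three stronger readings are tempting, and the documents do not support them.

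- **That early termination empties Part 3 from PKPOP.** The SAP was written with the termination known, yet it keeps multiple-dose concentration outputs (8.3.1), trough plots (8.3.4) and a Part 3 follow-up visit (9.3). Wholesale exclusion would make the PK outputs pointless. Protocol 4.5 also points to completion as staying in the study, not as finishing the drug.
- **That Part 2 non-returners were lost.** Protocol 5.2.4.1 says: "The cohort of subjects selected for Part 2 will not attend the Follow-up Visit following their first treatment period (Part 1"). SAP 3.3.2 says: "Part 2: 6 subjects returned to received the same" dose. If that cohort had 8 subjects, 8 − 6 = 2 did not return; if it had 6, none. The cohort's size is hidden by redaction, and non-returners could have been on placebo, with no PK data. Protocol 4.5 and 11.6 also ask for follow-up assessments, as far as possible, on withdrawal or discontinuation of the study. It likewise remains an inference that this cohort's fasted profiles end at 192 h.
- **That the PK results are biased.** This would need departure to be related to exposure. Protocol 7.2 says that subjects withdrawn for causally related events are generally not replaced, so a route exists, but no such case is reported.

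**Conclusion.** The point holds as a minor defect in a definition. The completion condition is separate from evaluability, has no subject-level meaning in either document, and would remove usable Cmax and AUC0-24h values from the summaries, and Cmax from the Part 1 power model, for any active subject who left early. Safety analyses use a different set and are untouched.

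The number affected is not stated and may be zero. If one active Part 1 subject were excluded, the slope interval would widen by about 0.1% to 5%, given the assumed dose spacing and the assumed active numbers in the two smaller cohorts. If departure is unrelated to exposure, the cost is precision only.

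**What to change.** In SAP section 5, delete the completion condition and define PKPOP as all subjects who received MT-6345 and have at least one evaluable PK parameter. Leave the emesis rule, including the option to analyse those data separately, as it is.

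Add that evaluability is judged for each parameter. Keep Cmax and AUC0-24h (or AUC0-τ in Part 3) whenever sampling covers them. Set the criteria for AUC0-last, AUC0-∞, the linearity factor and the accumulation ratio in the PK data-handling document of SAP 7.4, before unblinding. Record the departure from Protocol 10.2 in SAP section 10. SAP section 1 already gives the SAP precedence over the protocol on statistical analysis.

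The cost is one definition, a short list of criteria and one line in section 10, with no new data. Partial profiles will need parameter-level flags, and n will differ between parameters within a table. SAP 6.1 already reports N and n separately, so the table layout need not change.
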